#### Processing of Sera

Immediately after collection, the blood specimen tube will be made to stand upright to clot at room temperature before transport to the laboratory at Pasteur Institute. At the laboratory, specimens will be centrifuged before division.

#### Division of Sera

Serum specimens for anti-influenza serologic assays will be divided. Specimen division should be performed for only one participant at a time to avoid mixing blood tubes. Each serum specimen will be divided into 4 aliquots as follows:

- 1st aliquot: 0.6 mL for HAI assay
  - 2nd aliquot: 0.6 mL for back up 1 for HAI assay
  - 3rd aliquot: 0.6 mL for back up 2 for HAI assay
  - 4th aliquot: the remaining serum sample for back up and archive
- The study participant number, date of collection, blood specimen number, number of divisions obtained, and the date and time of division will be specified on a serologic specimen log form. On this form, comments may be made on the quality of specimens (e.g., hemolyzed, contaminated, etc.).

#### Conditions for Transport and Storage of Sera

Serum specimens for anti-influenza serologic assays will be immediately put in the freezer equal or lower than  $-20^{\circ}\text{C}$  after division and stored at this temperature until use. All handling will be done to prevent unnecessary freeze-thaw cycles (i.e., back-up samples should not be thawed unless required for testing). Temperature monitoring will be done to assure maintenance of cold chain and specimen quality.

#### Urine Specimens

Urine will be collected for pregnancy testing on visit S1/D1 (prior to vaccination). If D1 is conducted separately from S1, a urine pregnancy test should be done at each visit and prior to vaccination on D1.

No urine specimens will be stored after testing.

## 10 Assessment of Safety and Adverse Events

### 10.1 Adverse Events

An Adverse Event is any unfavorable and unintended sign (including a designated out-of-range laboratory finding), symptom, or disease temporally associated with the use of a study product, whether or not considered related to the product. The occurrence of an AE might come to the attention of study personnel during study visits and interviews of a study participant presenting for medical care. Information to be collected on AEs includes event description, time of onset, clinician's assessment of severity, relationship to study product, and time of resolution/stabilization of the event. AE assessment should be made only by those with the training and authority to make a diagnosis.

Any medical condition that was present at the time that the participant was enrolled should not be reported as an AE, but should be reported as a pre-existing condition on the Medical History Form. However, if this condition occurs with greater frequency or severity during the study, it should be recorded as an AE

#### 10.1.1 Solicited Local and Systemic Adverse Events

- Solicited adverse events are pre-specific local and systemic adverse events that are common or known to be associated with vaccination that are actively monitored as indicators of vaccine reactogenicity. Investigators will not be required to assess causality of solicited adverse events if the onset is during the solicitation periods. If a solicited adverse event progresses beyond the solicited period, it will continue to be reported as a solicited adverse event. If the solicited adverse event occurs after the solicitation period it will be reported as an unsolicited AE.
- For this trial, solicited local and systemic AEs will be assessed by study staff 30 minutes after vaccination then daily for 7 days by the participants. Participants will be provided a thermometer, ruler and a diary to record the presence or absence of solicited AEs, severity of the solicited AE and use of concomitant medication. The severity of the solicited local and systemic adverse events will be graded using the Toxicity Table for Grading Adverse Events ([Appendix A](#)). The specific solicited local and systemic adverse events that will be reported for this trial are:
  - **Solicited local adverse event (at site of injection):**
    - Erythema / redness – based on size in cm
    - Swelling / induration (hardness at site of injection ) – based on size in cm
    - Pain

- **Systemic Reactions:**

- Fever--Body temperature
- Fatigue/malaise
- Generalized muscle aches
- Joint aches
- Chills
- Nausea
- Vomiting
- Headache

#### **10.1.2 Unsolicited Adverse Events**

Unsolicited adverse events are any AEs that occur any time after the vaccine/placebo is given (temporally related to study product), whether or not deemed “related” to the product, and are not solicited (specifically asked of the participant). Unsolicited AEs can be observed by study staff while the participant is at a clinic for a study visit or reported by the participant at any time. Any sign or symptom that would normally be considered a “solicited AE” (for example, fever, nausea, injection site pain) starting after 7 days post-vaccination will be recorded as an unsolicited AE.

#### **10.2 Serious Adverse Events**

An SAE is defined as an AE that meets one of the following conditions:

- Death.
- Life-threatening (participant at immediate risk of death.) (The term “life-threatening” in the definition of “serious” refers to an event in which the patient was at risk of death at the time of the event; it does not refer to an event that hypothetically might have caused death if it were more severe).
- Requires inpatient hospitalization or prolongation of existing hospitalization.
- Results in congenital anomaly/birth defect. (Only in the case of a woman becoming pregnant during the study period after administration of at least one injection of study product. All pregnancies must be followed to term and outcome reported to IVAC and regulatory agencies.)

- Results in a persistent or significant disability or incapacity.
- Important medical events that might not result in death, be life-threatening, or require hospitalization might be considered SAEs when, based upon appropriate medical judgment, the event might jeopardize the well-being of the participant and require medical or surgical intervention to prevent one of the outcomes listed above. (Medical and scientific judgment should be exercised in deciding whether reporting these events is appropriate.)

All SAEs must be reviewed and evaluated by a study clinician to determine relationship to study vaccine as outlined in [Section 10.5](#) and recorded on an SAE form and reported, as specified in [Section 10.9](#). All such SAEs should also be followed until satisfactory resolution or until the investigator deems the event to be chronic or the participant to be stable.

### 10.3 AE/SAE Reporting Period and Parameter

Safety events are reported from the time of study injection (Day 1) through completion of the study at Day 91. Specifically, solicited AEs to assess local and systemic reactogenicities will be collected at 30 minutes and then daily for 7 days thereafter. If a solicited AE starts during the 7 days post vaccination period and continues beyond the 7 days it will continue to be reported as a solicited AE. SAEs will be reported from Day 1 through the end of the study at Day 91. Unsolicited AEs will be reported from Day 1 to Day 22 inclusive.

### 10.4 Severity of Event

This study will use the Toxicity Table for Grading Adverse Events (see [appendix A](#)). For events not included in the table, the following guidelines will be used to quantify intensity not included on the table, the following guidelines will be used to quantify intensity:

Grade	Description for grading when an event is not on Toxicity Table
1 (Mild)	Mild symptoms causing no or minimal interference with usual social & functional activities with intervention not indicated.
2 (Moderate)	Moderate symptoms causing greater than minimal interference with usual social & functional activities with intervention indicated.
3 (Severe)	Severe symptoms causing inability to perform usual social & functional activities with intervention or hospitalization indicated.
4 (Life threatening)	Potentially life-threatening symptoms causing inability to perform basic self-care functions with intervention indicated to prevent permanent impairment, persistent disability, or death.

**Basic Self-care Functions – Adult:** Activities such as bathing, dressing, toileting, transfer/movement, continence, and feeding.

**Usual Social & Functional Activities – Adult:** Activities which adults perform on a routine basis and those which are part of regular activities of daily living, for example going to work, shopping, cooking, use of transportation or pursuing a hobby.

#### Changes in Severity of an Event

Changes in the severity of an AE should be documented to allow an assessment of the duration of the event at each level of intensity to be performed. AEs characterized as intermittent require documentation of onset and duration of each episode.

### **10.5 Relationship to Study Vaccines**

The clinician's assessment of an AE's relationship to study product is part of the documentation process. The clinician must determine whether there is a reasonable possibility that the investigational product(s) caused or contributed to an AE. It is essential to have the best assessment possible as to whether adverse events are related to investigational products.

The relationship assessment, based on clinical judgment, should rely on the following:

- A temporal (time-based) relationship between the event and administration of the investigational product
- A plausible biological mechanism for the investigational product to cause the AE
- A possible alternative etiology for the AE
- Previous reports of similar AEs associated with the investigational product or other vaccines in the same class

To help assess, the following guidelines will be used:

Related – There is a reasonable possibility that the study vaccine caused the AE. “Reasonable possibility” means that there is evidence to suggest a causal relationship between the study product and the AE.

Not Related – There is not a reasonable possibility that the administration of the study product caused the event.

Any solicited local or systemic reactogenicity that occurs during the 5-day period post-injection is automatically regarded as related.

## 10.6 Follow up of AE

All reported AEs should be followed until resolution or stabilization, or until the participant's participation in the study ends. Participants who have an ongoing study product-related SAE at study completion or at discontinuation from the study will be followed by the PI or his designee until the event is resolved or determined to be irreversible, chronic, or stable by the PI.

## 10.7 General Guidelines for Recording AEs

To improve the quality and precision of acquired AE data, the PI should observe the following guidelines:

- Whenever possible, use recognized medical terms when recording AEs on the AE CRF. Do not use colloquialisms and/or abbreviations.
- If known, record the diagnosis (i.e., disease or syndrome) rather than component signs, symptoms and laboratory values on the AE CRF (e.g., record congestive heart failure rather than dyspnea, rales, and cyanosis). However, signs and symptoms that are considered unrelated to an encountered syndrome or disease should be recorded as individual AEs on the CRF (e.g., if congestive heart failure and severe headache are observed at the same time, each event should be recorded as an individual AE).
- AEs occurring secondary to other events (e.g., sequelae) should be identified by the primary cause. A "primary" AE, if clearly identifiable, generally represents the most accurate clinical term to record on the AE CRF. If a primary serious AE (SAE) is recorded on an SAE CRF, events occurring secondary to the primary event should be described in the narrative description of the case.

For example:

Orthostatic hypotension → Fainting and fall to floor → Head trauma → Neck pain

The primary AE is orthostatic hypotension.

- Death is an outcome of an event. The event that resulted in the death should be recorded and reported on the SAE CRF.
- For hospitalizations for surgical or diagnostic procedures, the illness leading to the surgical or diagnostic procedure should be recorded as the SAE, not the procedure itself. The procedure should be captured in the case narrative as part of the action taken in response to the illness.
- Pregnancies are not considered AEs. Participants will be instructed to notify the study team if they become pregnant during the course of the study. They will be recorded on a separate Pregnancy CRF. Pregnancy outcomes that include stillbirth and any congenital anomalies must be reported as SAEs.

## 10.8 Unexpected Allergic Reaction

### Immediate Reactions (within 30 minutes)

All participants will be observed for 30 minutes after administration of study product, with appropriate medical treatment readily available in case of an anaphylactic reaction following the administration of study product. Immediate reactions will be assessed by a study physician or appropriately trained medical staff. All reactions that occur during this time will be recorded on the CRF. Any immediate reaction which meets the criteria for an SAE must also be documented on an SAE form.

Emergency medicines will be available at the study clinic to be ready to give first aid if any adverse reactions or events should occur among any participant participating in this research. If anaphylaxis occurs after vaccination, it must be treated in accordance with current MOH regulations on handling anaphylaxis. Treatment for mild reactions after vaccination will be per "Guidance on the treatment of post injection reactions" issued under the Decision No 2535 by Ministry of Health, Vietnam (17). The applied treatment methods must be recorded and kept in the participant file. .

## 10.9 Reporting Procedures

### 10.9.1 Serious Adverse Events

All SAEs must be documented and reported to IVAC or its designate, even if the investigator considers that the SAE is not related to treatment. The study clinician will complete a **Serious Adverse Event Form** within the following timelines of such events:

- All deaths and immediately life-threatening events, whether related or unrelated, will be recorded on the Serious Adverse Event Form and sent by fax or email within 24 hours of site awareness.
- SAEs other than death and immediately life-threatening events (i.e., events resulting in hospitalization or prolongation of hospitalization; persistent or significant disability or incapacity, or other significant events determined by the investigator to be SAEs), regardless of relationship, will be reported via email or fax by the site within 24 hours of becoming aware of the event.

IVAC will be primarily responsible for medical monitoring of serious adverse events documented by the investigator. Investigator and PI HCM City will be responsible for reporting the SAEs to local regulatory authorities in accordance with local regulatory safety reporting guidelines. Medical Officers from PATH serving as technical consultants will review all serious adverse events and provide guidance regarding SAE management including classification and reporting. Details for review of serious adverse events and other unanticipated problems will be in an SOP drafted prior to study initiation.

### **10.9.2 Reporting of AEs**

Collected SAEs and AEs will be reported to responsible ethical review committees according to their requested timelines. An SOP for reporting to the responsible committees will be developed with reporting requirements and timelines prior to study initiation. It will be the investigator's responsibility to assure that all reportable events are reported to the proper authority or to IVAC and/or its designate in a timely manner and according to the SOP. PATH technical consultants may assist the investigator with regulatory reporting, per the finalized SOP.

### **10.9.3 Other Unexpected Issues/Unanticipated Problems**

During study process, if there are any problems related to the trial (unanticipated problems), the Principal Investigator is responsible for reporting to IVAC and PATH to discuss reasonable ways of handling the problem. The Principal Investigator is responsible for reporting any unanticipated problems that affect the health, welfare or rights of study participants or that may impact the integrity of the study data to the ethics committees involved in the review of the research. The Principal Investigator should maintain written documentation of all unanticipated problems and their reporting and resolution.

### **10.9.4 Reporting of Pregnancy**

Although women are not tested for pregnancy after vaccination and women are supposed to use effective birth control until Day 22, it is possible that a woman could report a pregnancy during the study. All pregnancies detected among women enrolled in the trial who receive study product must be reported on a Pregnancy Report CRF. All pregnancies must be followed to term and outcome reported to IVAC and regulatory agencies. Unblinding of allocation of treatment of female participants who become pregnant will not occur until after study completion, unless medically indicated.

## **11 Safety Oversight**

### **11.1 Protocol Safety Review Team**

Routine safety monitoring will be conducted by the Protocol Safety Review Team (PSRT). The PSRT will comprised of at least 4 members: the sponsor Medical Monitor, PATH Medical Officer/s, Contract Research Organization (CRO) Pharmacovigilance Medical Monitor and protocol Principal Investigator (or designate). PSRT members are selected based of their experience and expertise in the conduct and safety oversight of vaccine clinical trials.

During the vaccination phase of the trial, the PSRT reviews blinded cumulative solicited local and systemic reactions and AEs on a weekly basis. Frequencies of review post the vaccination phase will be at the discretion of the PSRT but no less than once a month.

### 11.1.1 Expedited Safety Review

Safety events listed in [table 1](#) require expedited PSRT review within 36 hours of submission of the safety information to data management and or SAE reporting system. Members of the PSRT will be notified of these events through the CRO pharmacovigilance system.

Event and relationship to study agent as assessed by investigator or CRO Pharmacovigilance Medical Monitor	Severity Grade
SAE, related	All grades
Unsolicited AE, related	4
Local reactions – erythema or induration	4

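### The 36-hour PSRT review list in 11.1.1 leaves out Grade 4 solicited systemic reactions and injection-site pain; the firm gap is an oral fever of 40.0 °C or more in Days 1–7 that is not brought under the SAE row

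*Combined protocol and SAP*

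**What the plan says.** Protocol 11.1.1 says that listed events "require expedited PSRT review within 36 hours of submission of the safety information to data management and or SAE reporting system". The list has three rows:

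- SAE, related: all grades.
- Unsolicited AE, related: Grade 4.
- "Local reactions – erythema or induration": Grade 4.

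The column header lets either the investigator or the CRO's pharmacovigilance medical monitor make the assessment.

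Otherwise, section 11.1 says that during the vaccination phase "the PSRT reviews blinded cumulative solicited local and systemic reactions and AEs on a weekly basis". After that phase the PSRT sets its own frequency, with a floor of once a month. Section 2.5.1 describes the meetings as generally weekly, for data up to Day 22.

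Section 10.1.1 lists fever, fatigue/malaise, muscle aches, joint aches, chills, nausea, vomiting, headache and injection-site pain as solicited. An event that begins in the solicited week stays solicited even if it continues. Under 10.1.2 the same kind of symptom "starting after 7 days post-vaccination will be recorded as an unsolicited AE". Appendix A and SAP 17.2.1 set Grade 4 fever at 40.0 °C or more for non-axillary readings, and section 9.1.1 specifies an oral thermometer.

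**The concern.** Whether the PSRT sees a Grade 4 reaction within 36 hours depends on how the event is collected and on a seriousness judgement, not on its grade. The list is also uneven. Grade 4 erythema or induration gets its own row by grade, although Appendix A defines it by potentially life-threatening consequences, so it would often be an SAE already. Fever, which can reach Grade 4 without being an SAE, has no row.

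The PSRT is the named oversight body, with no DSMB (11.2) and no formal pause rules. Section 11.1.2 ties a PSRT-initiated pause to its weekly or expedited reviews. So 11.1.1 decides which events reach that body before its next routine meeting.

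**Working it through.** **Step 1. Trace an oral fever of 40.0 °C or more on Day 3.**

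- Grade: 4, by temperature alone (Appendix A; SAP 17.2.1).
- SAE row: applies only if the event is classed as an SAE and related. Under 10.2, life-threatening means actual risk of death at the time, so the temperature does not qualify by itself. Hospitalization or judgement as an important medical event could qualify it.
- Unsolicited row: does not apply, because onset is in Days 1–7.
- Local row: does not apply.

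What remains is routine review. The same fever starting on Day 9 and judged related is a Grade 4 unsolicited AE and gets 36-hour review.

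**Step 2. The other solicited reactions at Grade 4 (Appendix A; 10.4 where Appendix A has no row).**

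| Reaction | What Grade 4 requires | Likely route |
|---|---|---|
| Fatigue/malaise, joint pain | Loss of basic self-care | May be an SAE ("Results in a persistent or significant disability or incapacity", or an important medical event), by judgement |
| Headache, injection-site pain | Loss of basic self-care, or hospitalization indicated; for headache also impaired alertness or neurologic function | An actual admission is an SAE; otherwise by judgement |
| Muscle aches | No Appendix A row; 10.4 requires intervention to prevent permanent impairment, disability or death | Close to the important-medical-event criterion |
| Nausea, vomiting | Life-threatening consequences | Normally an SAE |
| Chills | No Grade 4 | Not applicable |

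Once classed as an SAE, an event that is neither fatal nor immediately life-threatening, "regardless of relationship, will be reported via email or fax by the site within 24 hours of becoming aware of the event". The fatal and immediately life-threatening ones have the same 24-hour limit. If related, either kind then gets 36-hour PSRT review. Fever is therefore the firm gap, and the others depend on judgement.

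**Step 3. Extra wait after submission, during the vaccination phase.** Inputs: 36 h = 1.5 days; weekly = 7 days.

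- Largest: 7 − 1.5 = 5.5 days.
- Average, with the weekly wait W uniform on 0–7 days: 3.5 − 1.5 = 2.0 days.
- Counting only cases where 36 hours comes first, the mean of max(0, W − 1.5) is 5.5² / (2 × 7) = 2.16 days.

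After the vaccination phase the floor is monthly, so 5.5 days is not an overall maximum. Under uniform accrual, those dosed in the last 6 days of enrolment have part of Days 1–7 in that period: 252 × 6/21 = 72 in Phase 2 and 636 × 6/35 = 109 in Phase 3.

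**Step 4. How rare is it?** The Phase 1 trial had no fever in 30 vaccinees (2.1.6). Protocol Table 11 gives Grade 3 fever, above 102.2 °F, in 0.2% of 1,392–1,394 recipients of a licensed split vaccine.

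- (102.2 − 32) / 1.8 = 39.0 °C.
- 0.2% corresponds to 3 events: 3/1,393 = 0.215%, exact 95% CI 0.044% to 0.628%.
- Applied to 740 IVACFLU-S recipients: 740 × 0.002 = 1.48 with fever above 39.0 °C, range 0.3 to 4.6 from the interval.

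Fever of 40.0 °C or more is a subset of these, so one or none is likely.

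**Step 5. When does the clock start?** It starts at submission, not onset. Diary data are entered at the Day 8 visit (8.2.2), and the Day 2/Day 5 Contact form in the annotated CRF holds only a date and a yes/no. An event that does not surface earlier is submitted late whatever the list says. Adding a row without a site reporting rule would therefore do little for it.

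**The case against.** The case for leaving the list alone has weight.

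- **Second assessor.** The CRO medical monitor, who also sits on the PSRT, can bring an event under the list. So can the investigator, who has a PSRT seat as well.
- **Earlier detection.** Suspected Grade 3 or higher reactions reported at the Day 2 or Day 5 contact prompt a return to clinic (8.2.1). The 30-minute and unscheduled-visit forms grade temperature up to 4. For unanticipated problems, "the Principal Investigator is responsible for reporting to IVAC and PATH to discuss reasonable ways of handling the problem".
- **Phase 2 gate.** All Phase 2 safety data to Day 8 are reviewed before Phase 3 starts, that is, before 636 of 888 participants (72%) are dosed.
- **Suspension powers.** The sponsor, the Ministry of Health, an ethics committee or the investigator may suspend the trial at any time for a safety concern (6.2).
- **Rationale.** Solicited reactions are expected and actively followed in the first week, whereas Days 9–21 have no scheduled visit. A different trigger for the two periods is defensible, and no rule in the documents is broken.

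All of this stands and keeps the consequence small. None of it sets a deadline for PSRT review of a Grade 4 fever in Days 1–7. A safety monitoring plan (Appendix B) and an SOP on reviewing SAEs and unanticipated problems (10.9.1) are mentioned but not supplied; either may already set one.

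A reader might infer that every Grade 4 systemic reaction escapes prompt review, or that dozens more people would be dosed during the wait. The documents support neither. Most of the other Grade 4 definitions lead to, or close to, an SAE criterion, and a PSRT review does not itself stop dosing.

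**Conclusion.** The point holds as a minor, inexpensive improvement. On the protocol text, an oral fever of 40.0 °C or more starting in Days 1–7, and not brought under the SAE row by the investigator or the CRO medical monitor, has no 36-hour trigger, while the same related fever starting later does. Grade 4 headache, fatigue/malaise, joint pain and injection-site pain may also miss the trigger, but that depends on seriousness judgements.

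The size rests on three assumptions: that the licensed vaccine's fever rate carries over, that events fall at random within the weekly cycle, and that no unsupplied plan or SOP already sets a deadline. No effect on endpoints, sample size or error rates is claimed.

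**What to change.** 1. Add oral fever of 40.0 °C or more to the 11.1.1 list; preferably widen the Grade 4 local row to all solicited local and systemic reactions.
2. State that the row applies regardless of relatedness. Sections 10.5 and 13.7 disagree: 10.5 makes solicited reactions automatically related for 5 days, while 13.7 treats all solicited AEs as related.
3. Require sites to submit any such event within 24 hours of awareness, whether it surfaces at the 30-minute observation, a Day 2 or Day 5 contact, a recall or an unscheduled visit, without waiting for Day 8 diary entry. The diary's symptom scale stops at severe, so a clinician must assign functional Grade 4; fever can be read from the recorded temperature.
4. Editorial: 11.1.1 refers to table 1, which is the schedule of events. Point it to the list beneath.

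Cost: an amendment with ethics approval, brief site training, a small reporting step and a few more expedited notices. It uses the existing PSRT and CRO notification route. If the safety monitoring plan already covers this, only 11.1.1 needs aligning.
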